#### **12.4.1** Individual Laboratory Measurements and Abnormal Laboratory Values

#### Table 4: Clinical Laboratory Reference Ranges and Toxicity Grading Scales (Continued)

Laboratory AEs	Reference Ranges	Mild (Grade 1)	Moderate (Grade 2)	Severe (Grade 3)			
Albumin decrease, Female, 18-30Y - g/dL	3.9 - 5.0	3.8 - 3.5	2.0-2.9	<2.0			
Albumin decrease, Male, 31-50Y – g/dL	4.0 - 5.0	3.9 - 3.5	2.0-2.9	<2.0			
Albumin decrease, Female, 31-50Y – g/dL	3.8 - 4.8	3.7 – 3.5	2.0-2.9	<2.0			
AST increase – U/L	0-40	41 - 80	81 - 120	>120			
ALT increase, male – U/L	0-44	45-88	89 - 132	>132			
ALT increase, female – U/L	0 - 32	33 - 64	65 - 96	>96			
Alkaline phosphatase (AP) increase, males 18-20Y - U/L	51 - 125	126 - 250	251 - 375	>375			
Alkaline phosphatase (AP) increase, females, 18-20Y - U/L	42 - 106	107 - 250	251 - 375	>375			
Alkaline phosphatase (AP) increase, 21-150Y – U/L	44 - 121	122 - 250	251 - 375	>375			
Urine							
URINALYSIS by Dipstick							
Protein	negative / trace	1+	2+	>2+			
Blood (occult)	negative	1+	2+	>2+			
Glucose	negative	1+	2+	>2+			
URINE MICROSCOPY							
Red blood cells (RBC) per HPF	0 - 2	6-10	11-50	>50 and/or gross blood			
WBC (microscopic) – WBC per HPF	0 - 5	6-10	11-50	>50			
Bacteria (microscopic)	none / few	few	moderate	many			
Note 1: With the exception of AST ALT AP bilightin electrolytes urine protein BUN and creatining which should be within reference							

Note 1: With the exception of AST, ALT, AP, bilirubin, electrolytes, urine protein, BUN and creatinine, which should be within reference range, lab values of other analytes in the grade 1 range are acceptable for enrollment if (a) they are not considered to be clinically significant by the investigator and (b) there is no cluster of abnormal labs that combined are suggestive of an underlying disorder.

Note 2: Other Exceptions to screening laboratory tests' normal reference ranges are:

a. Racially based low total WBC or neutrophil counts up to toxicity Grade 1 are allowed, but toxicity Grades 2 or 3 are exclusionary. b.Labs performed as part of a panel but not listed above are to be recorded in the database. If abnormal, they are not exclusionary and are not to be graded per Toxicity table, however, the investigator would make a clinical decision about their clinical significance and, if clinically significant, they will be graded according to the criteria in Protocol Section 9.2.1. (Examples include mean corpuscular volume (MCV), mean corpuscular hemoglobin (MCH), mean corpuscular hemoglobin concentration (MCHC), red cell distribution width (RDW), mean platelet volume (MPV), and nucleated red blood cell count (NRBC CT), which are included in a CBC with differential.)

Note 3: If a participant was accepted into the trial with a laboratory value of an analyte that overlaps with values used for grading Grade 1 laboratory abnormalities, a TEAE will be reported if the on-study value of the same analyte increases to Grade 2 or higher.

Note 4: If the dipstick UA is abnormal, a microscopic UA will be performed, and the results will supersede the results of the dipstick UA.

Note 5: If the laboratory reports RBC/HPF as a range and not absolute values, then the range 3-10 will be graded as Grade 1. Note 6: Menstruating females with a positive dipstick UA or microscopic UA may be retested following cessation of menses.

Note 7: Isolated laboratory values that are outside the range of eligibility but are thought to be due to an acute condition or due to collection or laboratory error may be repeated once.

	• •			
Vital Sign AEs	Reference Ranges	Mild (Grade 1)	Moderate (Grade 2)	Severe (Grade 3)
Fever - °C Fever - °F	36.1 - 37.2  97.0 - 99.0 	37.3 - 38.4 99.1 - 101.1	38.5 - 38.9 101.2 - 102.0	>38.9 >102.0
Tachycardia - bpm	50 - 100 	101 - 115	116 - 130	>130 or ventricular dysrhythmias
Bradycardia – bpm	50 - 100 - 444	45 - 49	40 - 44	<40
Hypertension (systolic) - mmHg		131 - 150	151 - 160	>160
Hypertension (diastolic) - mmHg	130/89 2,3,4,5	90 - 95	96 - 100	>100
Hypotension (systolic) - mmHg		85 - 88	80 - 84	<80
Tachypnea – breaths per min	10 - 20 	21 - 25	26 - 30	>30
Note 1. No recent hot or col	d beverages or smoking A pr	otocol should select either 	C or  F for inclusion	

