#### 9.2.3 Procedures to be Followed in the Event of Abnormal Laboratory Test Values or Abnormal Clinical Findings

A licensed study clinician (listed on FDA Form 1572) will determine seriousness, severity, and causality of abnormal laboratory values; provide a medical evaluation of TEAEs; and classify TEAEs based upon medical judgment.

Abnormal laboratory values or clinical findings for all enrolled subjects after dosing will be assessed using the toxicity scales in Appendix B. Out of range values and findings noted at screening or baseline, but allowable for enrollment and dosing if within Grade 1, will only be considered TEAEs if their severity increases to Grade 2 or higher. For abnormalities noted from the time of study drug dosing, any Grade 1 or higher laboratory abnormality listed on the toxicity Table 3 in Appendix B will be entered in the database as a TEAE. Safety laboratory results that are reported as TEAEs will be evaluated by the CTU clinician as clinically significant (CS) or not clinically significant (NCS). Abnormal laboratory values, performed as part of HEM, COAG, CHEM, or UA but not listed in this toxicity table will be evaluated by the study clinicians, recorded in the source document and, if clinically significant, considered TEAEs and graded according to the criteria in Section 9.2.1.

Protocol-specific laboratory normal range values are included in the study-specific MOP and toxicity grades for evaluation of TEAEs are included in Appendix B, Table 3.

Gross blood in urine that is confirmed due to menses is not a TEAE (but is for all other reasons).

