#### Table 3: Toxicity Grading Tables – LABORATORY AEs
Laboratory AEs	Mild (Grade 1)	Moderate (Grade 2)	Severe (Grade 3)					
Urine								
URINALYSIS by Dipstick								
Protein	1+	2+	>2+					
Blood (occult)	1+	2+	>2+					
Glucose	1+	2+	>2+					
URINE MICROSCOPY								
Red blood cells (RBC) per HPF	3-10	11-30	>30 and/or gross blood					
White blood cells (WBC) per HPF	6-10	11-30	>30 and/or symptomatic urogenital infection					
Bacteria (microscopic)	few	moderate many						

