- The proportion of participants with abnormal laboratory results by parameter and timepoint will be summarized for CHEM (Table 27 for the Safety Population and Table 28 for the Safety Subset Population), HEM (Table 33 for the Safety Population and Table 34 for the Safety Subset Population), COAG (Table 39 for the Safety Population and Table 40 for the Safety Subset Population), and UA (Table 45 for the Safety Population and Table 46 for the Safety Subset Population).
- The proportion of participants with mild, moderate, or severe laboratory results by parameter and timepoint will be summarized for CHEM (Table 29 for the Safety Population and Table 30 for the Safety Subset Population), HEM (Table 35 for the Safety Population and Table 36 for the Safety Subset Population), COAG (Table 41 for the Safety Population and Table 42 for the Safety Subset Population), and UA (Table 47 for the Safety Population and Table 48 for the Safety Subset Population).
- Summary statistics of measurements and change from baseline by parameter and timepoint for CHEM (Table 31 for the Safety Subset Population and Table 32 for the Safety Population), HEM (Table 37 for the Safety Population and Table 38 for the Safety Subset Population), and COAG (Table 43 for the Safety Population and Table 44 for the Safety Subset Population). UA character results will be excluded from change from baseline summaries.
- Change from baseline at each scheduled timepoint will be visualized using box plots for each parameter. The safety population used for each figure will be noted in the title. UA character results will be excluded from graphical summaries.
  - CHEM: Beginning at Figure 7 and continuing through Figure 46
  - HEM: Beginning at Figure 47 and continuing through Figure 64

#### • COAG: Figure 65, Figure 66, Figure 67, Figure 68, Figure 69, and Figure 70

Screening laboratory results will be listed. Serology result will be shown in Listing 14. Urine drug and cotinine and alcohol breathalyzer test results will be shown in Listing 15. Pregnancy testing and FSH test results will be shown in Listing 16.

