### Table 26: Listing of Abnormal Laboratory Results - Urinalysis

[Implementation Note: This listing is included in the table shells document, as it is included in the body of the CSR. This listing includes all abnormal Urinalysis results (laboratory results outside of the normal range defined in the protocol). Normal urinalysis results for other parameters that occurred on the same visit as the abnormal result will not be listed. Results that are outside the normal range but not mild, moderate, or severe will have "(ONR)" included after the result. Similarly, results that meet grading criteria of mild, moderate, or severe but which are not treatment emergent (not worse than baseline) will be shown as ONR. Listing should be sorted by Cohort, Participant ID, Timepoint, and Parameter.]

Cohort	Participant ID	Sex	Age (years)	Planned Study Day	Actual Study Day	Laboratory Parameter (Units)	Result (Severity)	Clinical Significance	Relationship to Treatment	If Not Related, Alternate Etiology	Action Taken with Study Treatment	Participant Discontinued Due to Result?

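### SAP Table 4 puts urine bacteria 'few' in both the reference range and Grade 1, so a new post-dose 'few' is normal and Mild at the same time

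*SAP*

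**What the plan says.** SAP Table 4 sets its columns out as "Laboratory AEs Reference Ranges Mild (Grade 1) Moderate (Grade 2) Severe (Grade 3"). The bacteria row under urine microscopy is "Bacteria (microscopic) none / few few moderate many".

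Protocol Appendix B Table 3 has grade columns but no reference range column. Its row is "Bacteria (microscopic) few moderate many". Protocol section 9.2.3 says that the normal ranges are in the Manual of Procedures (MOP). For findings after dosing it states that "any Grade 1 or higher laboratory abnormality listed on the toxicity Table 3 in Appendix B will be entered in the database as a TEAE".

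SAP section 9.6 reports urinalysis in two parallel ways. Abnormal results by timepoint are in "UA (Table 45 for the Safety Population and Table 46 for the Safety Subset Population"). Mild, moderate and severe results are in "UA (Table 47 for the Safety Population and Table 48 for the Safety Subset Population"). Table 26 lists abnormal urinalysis results, which its shell defines as "laboratory results outside of the normal range defined in the protocol". Listing 12 prints each result with its severity grade beside the reference range.

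Note 3 to SAP Table 4 deals with participants enrolled with a value that overlaps Grade 1. For them "a TEAE will be reported if the on-study value of the same analyte increases to Grade 2 or higher".

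**The concern.** A grading table works only if its reference range and its grades exclude each other. In this row they do not: the single Grade 1 category is also one of the two normal categories. A programmer following the SAP has no rule for *few*. The abnormal-results tables and the toxicity tables, which describe the same samples, can then disagree.

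The overlap also reaches safety reporting. The protocol turns a new Grade 1 laboratory abnormality into a TEAE, and TEAE type and incidence is a secondary endpoint. A participant could be counted there for a result that the SAP's own range calls normal.

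**Working it through.** No arithmetic decides this point. The check compares the categories and then follows *few* through the outputs.

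**1. The row, category by category**

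| Microscopy result | SAP Table 4 reference range | SAP Table 4 grade | Protocol Table 3 grade |
|---|---|---|---|
| none | inside | not graded | not graded |
| few | inside | 1 | 1 |
| moderate | outside | 2 | 2 |
| many | outside | 3 | 3 |

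The reference set {none, few} and the Grade 1 set {few} share *few*, so Grade 1 lies wholly inside the reference range. The other three results are classified without conflict.

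**2. Is it an artefact of the text extraction?** No. The row fills all five columns, as its neighbours do. The other urine rows do not overlap: protein negative/trace against 1+, occult blood and glucose negative against 1+, RBC 0-2 against 6-10, WBC 0-5 against 6-10.

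**3. Do other rules resolve it?**
- *Few* already present at screening or baseline: protocol 9.2.3, SAP 9.6 and Note 3 make it a TEAE only if it reaches Grade 2. These rules limit TEAE reporting. They do not say what grade is shown in Tables 47 and 48.
- Menstruation: the urinalysis footnote to the schedule of events says that an abnormal urinalysis in a menstruating participant is not graded as a TEAE.
- New *few* after dosing, outside both situations: no rule applies. Microscopy follows only an abnormal dipstick, so a participant whose dipstick was normal before dosing has no earlier bacteria result.

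**4. Where a new post-dose *few* goes**
- Tables 47 and 48: Mild, by the grade column. These tables follow the layout of Tables 29 and 30, which have an any-parameter row and a maximum-severity row. A lone *few* would raise the Mild count in those summary rows too.
- Tables 26, 45 and 46: not abnormal, if the Table 4 reference range is the one applied.
- Listing 12: could print *few* as Mild beside a reference range that contains *few*.
- TEAE data: entered, under protocol Table 3 with section 9.2.3.

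**5. Ceiling on the number.** There are 3 scheduled post-dose urinalyses (24 h, 48 h, Day 14). With 20 participants that is 20 × 3 = 60; if cohort T5 is not enrolled it is 16 × 3 = 48. Only samples with an abnormal dipstick go to microscopy, and only some of those would read *few*. The documents give neither rate.

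**The case against.** The strongest reply is that the protocol governs TEAE reporting and is consistent on this row: *few* is Grade 1, and a new post-dose Grade 1 laboratory abnormality is a TEAE. On that view the only fault is one SAP reference cell. This stands, and it limits what can be said. A reader might infer that these would be false TEAEs. That presumes the SAP reference cell is right, and nothing in the documents shows that.

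A second reply is that *few* may still appear in Tables 26, 45 and 46. The Table 26 shell refers to a range defined in the protocol, but the protocol gives none for this row and points to the MOP, which is not among the documents. SAP 9.6 describes abnormal results as including those outside the normal range, which leaves room to treat a graded result as abnormal. Tables 45 and 46 state no cut-off. The omission of *few* from these outputs is therefore the likely reading, not a certain one. The contradiction between the reference and grade columns of Table 4 remains either way.

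A third reply is that a normal result is not an abnormality and so is never graded. Then the Grade 1 cell can never be used, while protocol Table 3 still grades *few*. The text needs an edit on this reading as well.

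Finally, the effect is minor. That is true. The female creatinine row of the same table has a similar overlap (reference 0.57-1.00, Grade 1 0.58-1.50 mg/dL) on a renal marker, but that is a separate point and does not remove this one.

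**Conclusion.** The inconsistency is real and minor. As written, a new post-dose *few* is within the SAP's normal range, Mild in Tables 47 and 48, and a TEAE under the protocol. The conclusion rests on the text of SAP Table 4 and protocol Table 3, and on the absence of any rule for a *few* that is new after dosing. Its effect on Tables 26, 45 and 46 assumes in addition that the Table 4 range is the one applied there.

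The number of affected results is at most a small part of the 60 scheduled post-dose urinalyses and cannot be estimated from the documents. It would be going too far to infer that the whole row gives contradictory counts, since only *few* does. No primary endpoint is affected. The systemic and laboratory halting criteria need a related SAE or related events of Grade 2 or higher, so a Grade 1 *few* does not meet them.

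**What to change.** Reconcile SAP Table 4 with protocol Appendix B Table 3 so that *few* falls in one category only. Then use that category in Tables 26 and 45 to 48, in Listing 12 and in TEAE reporting. State which reference range Tables 26, 45 and 46 apply to this row, because the protocol does not give one.

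The smallest edit is to the SAP reference cell, which would bring the SAP into line with the protocol grade. SAP section 15 allows an addendum before final data lock. If the sponsor decides instead that *few* should not be graded, the protocol table changes too, and that needs an amendment. Which category applies is the sponsor's clinical decision.

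The cost is about one cell per table. Nominal Grade 1 or abnormal-result counts for bacteria may shift slightly, depending on the choice.

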#### Table 5: Vital Signs Toxicity Grading Scales

Note 1: No recent hot or cold beverages or smoking. A protocol should select either oC or oF for inclusion

Note 2: Assume awake and in supine position for 5 min at rest. For TEAE, measurements at least 3 times with 2 concordant results (See Protocol Section 8.1.6)

Note 3: Abnormal HR and BP on first measurement may be repeated twice more with the participant resting between measurements for at least 5 min (See Protocol Section 8.1.6).

Note 4: Exceptions to screening BP and HR reference range are:

(a) Participants with baseline  $HR \ge 45$  to 50 bpm may be accepted if they do not have symptomatic bradycardia, including syncope, heart disease. ECG abnormalities, or history of syncope or use of medication

(b) Participants with baseline SBP up to 140 mmHg and DBP up to 90 mmHg may be accepted if they do not have MH of symptomatic hypertension, including paroxysmal hypertension, heart disease, renal disease, CNS disease, visual abnormalities or evidence of peripheral vascular disease, ECG abnormalities, use of medication, use of illicit drugs or FH of hypertension

Note 5: Isolated/individual abnormalities of VS would not be considered toward halting criteria. Abnormalities of VS will be described as "increased X" or "decreased X" (X = HR, BP, RR, temperature) if asymptomatic, transient and not associated with a systemic or organ-specific disorder and coded by MedDRA within the System Organ Class (SOC) "Investigations." These abnormalities will be graded per criteria in this table, but not considered in determining whether study stopping criteria have been met. On the other hand, abnormalities of VS that are either secondary to systemic or organ-specific clinical syndrome or primary disorders will be coded in the appropriate SOC (e.g., "cardiac disorders", respiratory disorders", "immunological disorders", etc.). These abnormalities will be considered in determining whether stopping criteria have been met.

#### 12.4.1 Individual Laboratory Measurements and Abnormal Laboratory Values

#### Table 4: Clinical Laboratory Reference Ranges and Toxicity Grading Scales (Continued)

#### Table 6:ECG Toxicity Grading Scale

ECG interval abnormality	Reference range	Grade 1	Grade 2	Grade 3
QTcF interval prolonged (msec): • Male • Female	• ≤450 msec • ≤470 msec	Asymptomatic, QTcF • 451 - 479 msec • 471 - 479 msec	Asymptomatic, QTcF 480-500 msec OR increase in interval 30-59 msec above baseline	Asymptomatic, QTcF >500 msec OR increase in interval ≥60 msec above baseline
PR interval prolonged (msec)	≤210 msec	211-250 msec	>250 msec	Type II 2 nd degree AV block OR ventricular pause >3.0 sec

Note 1: Events will be coded as treatment-emergent SAEs if there are life-threatening associated symptoms or signs (arrhythmia, CHF, hypotension, syncope, TdP, etc.).

Note 2: If a male participant was accepted into the trial with a QTcF value that overlaps with values used for grading Grade 1 QTcF prolongation, a TEAE will be reported if the QTcF value is higher than the baseline value.

#### **10.2 Protocol Deviations**

#### Table 7: Distribution of Protocol Deviations by Category, Type, and Cohort – All Enrolled Participants

[Implementation Note: Only deviations reported during the course of the study will be included.]

		Coh (N=	ort 1 =X)	Coh (N	Cohort 2 (N=X)		Cohort 2 (N=X)		Cohort 2 (N=X)		Cohort 2 (N=X)		Cohort 3 (N=X)		ort 4 X)	Cohort 5 (N=X)		All Participants (N=X)	
Category	Deviation Type	No. of Subj.	No. of Dev.	No. of Subj.	No. of Dev.	No. of Subj.	No. of Dev.	No. of Subj.	No. of Dev.	No. of Subj.	No. of Dev.	No. of Subj.	No. of Dev.						
Eligibility/enrollment	Any type	х	х	х	х	X	х	х	х	x	x	х	x						
	Did not meet inclusion criterion																		
	Met exclusion criterion																		
	ICF not signed prior to study procedures																		
	Other																		
Treatment administration schedule	Any type																		
	Out of window visit																		
	Missed visit/visit not conducted																		
	Incomplete treatment administration																		
	Delayed treatment administration																		
	Other																		
Follow-up visit schedule	Any type																		
	Out of window visit																		
	Missed visit/visit not conducted																		
	Other																		
Protocol procedure/assessment	Any type																		
	Incorrect version of ICF signed																		
	Blood not collected																		

#### **10.2 Protocol Deviations**

#### Table 7: Distribution of Protocol Deviations by Category, Type, and Cohort – All Enrolled Participants (*Continued*)

		Coho (N=	ort 1 =X)	Cohort 2 ( (N=X)		Cohort 2 (N=X)		Cohort 3 (N=X)		Cohort 3 (N=X)		Cohort 4 (N=X)		Cohort 5 (N=X)		All Participants (N=X)	
Category	Deviation Type	No. of Subj.	No. of Dev.	No. of Subj.	No. of Dev.	No. of Subj.	No. of Dev.	No. of Subj.	No. of Dev.	No. of Subj.	No. of Dev.	No. of Subj.	No. of Dev.				
	Urine not collected																
	Other specimen not collected																
	Too few aliquots obtained																
	Specimen result not obtained																
	Required procedure not conducted																
	Required procedure done incorrectly																
	Study product temperature excursion																
	Specimen temperature excursion																
	Other																
Treatment administration	Any type																
	Required procedure done incorrectly																
	Study product temperature excursion																
	Other																
Note: N = Number of participants of	enrolled.																

#### 14.1 Description of Study Participants

#### 14.1.1 Disposition of Participants

#### Table 8: Participant Disposition by Cohort – All Enrolled Participants

	Coh (N=	ort 1 =X)	Coh (N=	ort 2 =X)	Coh (N=	ort 3 =X)	Coh (N=	ort 4 =X)	Coh (N=	ort 5 =X)	All Part (N=	ticipants =X)
Participant Disposition	n	%	n	%	n	%	n	%	n	%	n	%
Screened											х	
Enrolled	х	100	х	100								
Started Infusion	х	xx	х	xx								
Completed Infusion a	х	XX	х	XX								
Completed Bronchoscopy with BAL	х	xx	х	xx								
Completed All PK Blood Draws	х	xx	х	xx								
Completed All Plasma Urea Blood Draws	х	xx	х	xx								
Completed Follow-up (Study Day 14) a	х	XX	х	xx								
Completed Final Study Visit (Study Day 30) a	х	XX	х	XX								
Early Termination a	х	xx	х	XX								
Note: N = Number of participants enrolled. a Refer to Listing 16.2.1 for reasons participants discontinued or terminated end	early.											

#### Table 9: Treatment Discontinuations or Early Terminations by Reason and Cohort – All Enrolled Participants

[Implementation Note: Only reasons for treatment discontinuation or early termination reported during the study will be included.]

	Coh (N	ort 1 =X)	Coh (N	ort 2 =X)	Coh (N=	ort 3 =X)	Coh (N=	ort 4 =X)	Coh (N=	ort 5 =X)	All Par (N=	ticipants =X)
Reason for Treatment Discontinuation or Early Termination	n	%	n	%	n	%	n	%	n	%	n	%
Treatment Discontinuation												
Serious Adverse Event (other than death)	x	100	х	100	х	100	х	100	х	100	х	100
Adverse Event, Other than Serious Adverse Event	x	xx	х	xx	х	xx	х	xx	х	xx	x	xx
Protocol Deviation	x	xx	х	xx	х	xx	х	xx	х	XX	х	xx
Withdrawal by Participant	x	xx	х	xx	х	xx	х	xx	х	XX	х	xx
Withdrawal by Investigator	x	XX	х	XX	х	xx	х	xx	х	XX	х	xx
COVID-19 Pandemic	x	xx	х	XX	х	xx	х	xx	х	XX	х	xx
Termination of Site by Sponsor	x	XX	х	XX	х	xx	х	xx	х	XX	х	xx
Termination of Study by Sponsor	x	XX	х	XX	х	xx	х	xx	х	XX	х	xx
Death	x	XX	х	XX	х	xx	х	xx	х	XX	х	xx
Technical Problems	x	XX	х	XX	х	xx	х	xx	х	XX	х	xx
Not Eligible at Enrollment	x	xx	х	xx	х	xx	х	xx	х	XX	х	xx
Became Ineligible After Enrollment	х	xx	х	xx	х	xx	х	xx	х	XX	х	xx
Failure to Receive the Entire Volume of Study Drug Infusion	x	xx	х	xx	х	xx	х	xx	х	XX	х	xx
Other	x	XX	х	XX	х	xx	х	xx	х	XX	х	xx
Early Termination												
Serious Adverse Event (other than death)	x	xx	х	xx	х	xx	х	xx	х	XX	х	xx
Adverse Event, Other than Serious Adverse Event	x	XX	х	XX	х	XX	х	XX	х	XX	х	XX
Protocol Deviation	х	XX	х	XX	х	XX	х	XX	х	XX	х	XX
	x	xx	х	XX	х	XX	х	XX	х	XX	х	XX
Note: N = Number of participants enrolled.												

Table 10: I	neligibility Summary	of Screen Failures
-------------	----------------------	--------------------

		Participant	ts Excluded									
Inclusion/Exclusion Category	Inclusion/Exclusion Criterion	n a	0⁄0 b									
Inclusion and Exclusion	Number of participants failing any eligibility criterion or eligible but not enrolled	Х	100									
Inclusion	Any inclusion criterion	Х	XX									
	[inclusion criterion 1]	X	XX									
	[inclusion criterion 2]	X	XX									
	[inclusion criterion 3]	X	XX									
Exclusion	Any exclusion criterion	X	XX									
	[exclusion criterion 1]	X	XX									
	[exclusion criterion 2]	Х	XX									
	[exclusion criterion 3]	X	XX									
Eligible but Not Enrolled	Any reason eligible but not enrolled	Х	XX									
	[reason 1]	Х	XX									
	[reason 2]	Х	XX									
	[reason 3]	Х	XX									
a More than one criterion may be mark b Denominator for percentages is the to	ted per participant. Detal number of screen failures.		·									
	Coh (N	ort 1 =X)	Col (N	nort 2 (=X)	Coh (N	ort 3 =X)	Coł (N	ort 4 =X)	Coh (N	ort 5 =X)	All Par (N	ticipants =X)
--	--	--	---	--	--	---	--	--	---	--	---	--
Reason Participants Excluded	n	%	n	%	n	%	n	%	n	%	n	%
Did not receive any amount of study product	х	xx	х	XX	х	xx	х	xx	х	xx	x	xx
Did not receive full amount of study product												
Any Reason												
Did not receive full amount of study product												
Did not undergo BAL at assigned sampling timepoint												
BAL return volume not adequate for analysis												
Has no measurable drug concentration for ELF or AM												
Any Reason												
Did not receive full amount of study product												
Has no measurable drug concentration in plasma												
Any Reason												
Excluded from Lung PK Analysis Population												
Excluded from Plasma PK Analysis Population												
Has protocol deviations that potentially impact PK												
Plasma PK and BAL PK data insufficient to estimate any PK parameters												
	Reason Participants ExcludedDid not receive any amount of study productDid not receive full amount of study productAny ReasonDid not receive full amount of study productDid not receive full amount of study productDid not undergo BAL at assigned sampling timepointBAL return volume not adequate for analysisHas no measurable drug concentration for ELF or AMAny ReasonDid not receive full amount of study productHas no measurable drug concentration in plasmaAny ReasonExcluded from Lung PK Analysis PopulationExcluded from Plasma PK Analysis PopulationHas protocol deviations that potentially impact PKPlasma PK and BAL PK data insufficient to estimate any PK parameters	Coh (NReason Participants ExcludednDid not receive any amount of study productxDid not receive full amount of study product	Cohort 1 (N=X)Reason Participants Excludedn%Did not receive any amount of study productxxxDid not receive full amount of study productAny ReasonDid not receive full amount of study productDid not receive full amount of study productDid not receive full amount of study productDid not undergo BAL at assigned sampling timepointBAL return volume not adequate for analysisHas no measurable drug concentration for ELF or AMDid not receive full amount of study productHas no measurable drug concentration in plasmaAny ReasonDid not receive full amount of study productHas no measurable drug concentration in plasmaAny ReasonExcluded from Lung PK Analysis PopulationHas protocol deviations that potentially impact PKPlasma PK and BAL PK data insufficient to estimate any PK parameters	Cohort 1 (N=X)Col (NReason Participants Excludedn%nDid not receive any amount of study productxxxxDid not receive full amount of study productAny Reason </td Cohort 1 (N=X)Cohort 2 (N=X)Reason Participants Excludedn%n%n%n%n%Did not receive any amount of study productxxxxxxDid not receive full amount of study productAny ReasonDid not receive full amount of study productDid not receive full amount of study productDid not undergo BAL at assigned sampling timepointBAL return volume not adequate for analysisHas no measurable drug concentration for ELF or AMDid not receive full amount of study productHas no measurable drug concentration in plasmaAny ReasonDid not receive full amount of study productHas no measurable drug concentration in plasmaAny ReasonExcluded from Lung PK Analysis PopulationHas protocol deviations that potentially impact PKPlasma PK and BAL PK data insufficient to estimate any PK parametersavaralled	Cohort 1 <math>(N=X)</math>Cohort 2 <math>(N=X)</math>Coh <math>(N)</math>Reason Participants Excludedn%n%nDid not receive any amount of study productxxxxxxxxDid not receive full amount of study productAny ReasonDid not receive full amount of study productDid not receive full amount of study product	Cohort 1 (N=X)Cohort 2 (N=X)Cohort 3 (N=X)Reason Participants Excludedn%n%n%Did not receive any amount of study productxxxxxxxxxxxDid not receive full amount of study productAny ReasonDid not receive full amount of study productDid not receive full amount of study product<	Cohort 1 (N=X)Cohort 2 (N=X)Cohort 3 (N=X)Coh (N=X)Did not receive full amount of stud	Colort 1 (N=X)Colort 2 (N=X)Colort 3 (N=X)Colort 4 (N=X)Reason Participants Excludedn%n%n%n%Did not receive any amount of study productxx	Color: 1 (N=X)Color: 2 (N=X)Color: 3 (N=X)Color: 4 (N=X)Color: 4 (N=X)<	Cover 1 (N=X)         Column 2 (N=X)         Column 3 (N=X)         Column 3 (N=X)         Column 3 (N=X)         Column 3 (N=X)         Column 3 (N=X)         Column 3 (N=X)           Reason Participants Excluded         n         %	Image: Contract in the second state in the	Cohort 1 (N=X)Cohort 2 (N=X)Reason Participants Excludedn%n%n%n%n%Did not receive any amount of study productxxxxxxDid not receive full amount of study productAny ReasonDid not receive full amount of study productDid not receive full amount of study productDid not undergo BAL at assigned sampling timepointBAL return volume not adequate for analysisHas no measurable drug concentration for ELF or AMDid not receive full amount of study productHas no measurable drug concentration in plasmaAny ReasonDid not receive full amount of study productHas no measurable drug concentration in plasmaAny ReasonExcluded from Lung PK Analysis PopulationHas protocol deviations that potentially impact PKPlasma PK and BAL PK data insufficient to estimate any PK parametersavaralled	Cohort 1 $(N=X)$ Cohort 2 $(N=X)$ Coh $(N)$ Reason Participants Excludedn%n%nDid not receive any amount of study productxxxxxxxxDid not receive full amount of study productAny ReasonDid not receive full amount of study productDid not receive full amount of study product	Cohort 1 (N=X)Cohort 2 (N=X)Cohort 3 (N=X)Reason Participants Excludedn%n%n%Did not receive any amount of study productxxxxxxxxxxxDid not receive full amount of study productAny ReasonDid not receive full amount of study productDid not receive full amount of study product<	Cohort 1 (N=X)Cohort 2 (N=X)Cohort 3 (N=X)Coh (N=X)Did not receive full amount of stud	Colort 1 (N=X)Colort 2 (N=X)Colort 3 (N=X)Colort 4 (N=X)Reason Participants Excludedn%n%n%n%Did not receive any amount of study productxx	Color: 1 (N=X)Color: 2 (N=X)Color: 3 (N=X)Color: 4 (N=X)Color: 4 (N=X)<	Cover 1 (N=X)         Column 2 (N=X)         Column 3 (N=X)         Column 3 (N=X)         Column 3 (N=X)         Column 3 (N=X)         Column 3 (N=X)         Column 3 (N=X)           Reason Participants Excluded         n         %	Image: Contract in the second state in the
